Study Protocol with Statistical Analysis Plan

Study Title: Post-operative Pain Control with Sphenopalatine Ganglion Nerve Block in
Septorhinoplasty Patients

NCT05667324

University of Florida Protocol ID: IRB202201279-A

Approved protocol date: 3/28/2023

IRB Protocol

1. Project Title: Post-operative pain control with sphenopalatine ganglion nerve block in septorhinoplasty patients

2. Investigator(s):

Principal Investigator: [name]

Co-Investigators:

[name]

[name]

[name] [name], DDS

[name], PHD

Study Coordinator: [name], PHD

Co-study coordinator: [name], CCRC

Other (faculty only listed):

[name]

[name]

[name]

[name]

[name]

[name], MS

[name]

[name]

[name]

[name]

3. Abstract:

Nasal septoplasty is a very common procedure performed by both otolaryngology and plastic surgery. This functional procedure is typically performed for nasal obstruction caused by septal deviation and may also be performed during aesthetic rhinoplasties or endoscopic sinus surgeries for greater exposure and access. Post-operative pain after septoplasty or septorhinoplasty, is generally mild with more moderate pain reported within the first 24-48 hours after surgery (1,2). Maxillary nerve blocks have been shown to significantly reduce post-operative pain within and analgesic intake during the 24-hour period following endoscopic sinus surgery (3, 4). This randomized, double-blinded, placebo-controlled study will investigate blocks of the pterygopalatine fossa bilaterally using a suprazygomatic approach. It is our hypothesis that this technique will result in decreased post-operative pain, post-operative opioid use, and the morbidity that is associated with it.

4. Background:

Nasal septoplasty is a very common procedure performed by both otolaryngology and plastic surgery (5). This procedure is commonly performed as a functional surgery to correct septal deviation and improve nasal obstruction but is also routinely performed along with aesthetic rhinoplasties. Notable post-operative complications include bleeding, septal hematomas, and septal perforations. Post-operative pain is generally mild following septoplasty or septorhinoplasty and is reported to be worse within the first 24-48 hours. Typical pain management following septoplasty or septorhinoplasty include narcotic and non-narcotic analgesics including oxycodone, hydrocodone, acetaminophen, and ibuprofen. Despite multimodal pain control, uncontrolled post-operative pain is reported and may be related to procedural complaints, delayed return to work and even hospital readmissions (4). The number of narcotic pain pills prescribed to patients can vary greatly. One study concluded that 11 opioid tablets were sufficient to control post-operative pain after septoplasty and rhinoplasty procedures (6), however, patients are typically prescribed a range of 20 – 30 pills post-operatively (7).

Maxillary nerve blocks have been shown to significantly reduce post-operative pain and analgesic use within the 24 hour period following endoscopic sinus surgery (3,4). It has also been described for pediatric cleft palate repair with excellent control of post-operative pain compared to systemic analgesics (8-11). The need for post-operative morphine was completely eradicated in one study (11) The effects of local anesthetic have been noted to have effects on pain for up to 10 days after injection, long after the local anesthetic wears off (8). The suprazygomatic approach to the pterygopalatine fossa is a technically easy procedure to perform with ultrasound guidance, with an average procedure time of 56 seconds (10). Suprazygomatic approaches to the pterygopalatine fossa have been associated with fewer complications than infrazygomatic approaches, which include orbital puncture, intracranial injection, maxillary artery puncture, or posterior pharyngeal wall injury (8). Using a suprazygomatic approach and ultrasound guidance, Sola et. al. experienced zero technical complications after 50 blocks (10).

Literature review produced no studies to date on the efficacy of suprazygomatic maxillary nerve blocks for the management of post-operative septorhinoplasty pain control. We currently perform SPG blocks in septorhinoplasty patients based on surgeon and anesthesiology discretion, as well as patients agreement on receiving block, but we currently do not have a standardized way of determining if pain is being controlled in a meaningful way, ie reducing the number the narcotics required post-operatively or reducing the PACU length of stay. Our aim is to conduct a prospective randomized controlled trial using bilateral suprazygomatic maxillary nerve blocks to control post-operative pain in adult patients undergoing septoplasty or septorhinoplasty. We hypothesize that using maxillary nerve blocks in adult patients is a safe and effective way to manage post-operative pain, decreasing complications, post-operative opioid use, and the morbidity that is associated with it.

5. Specific Aims:

The primary aims of this study are to demonstrate in a prospective, randomized, controlled trial, that the application of bilateral suprazygomatic maxillary nerve blockade can safely and effectively:

- 1) decrease the opioid requirement post-operatively

Secondary objectives are to demonstrate

- 1) a decrease in post-anesthesia care unit observation time
- 2) efficiency of SMS based survey for post-operative data collection

6. Research Plan:

PARTICIPANT SELECTION CRITERIA:

The PI and co-investigators already routinely do sphenopalatine ganglion nerve block in our septorhinoplasty patients. All patients undergoing septorhinoplasty who met the inclusion/exclusion criteria (see below) will be offered the opportunity to participate in the study. These patients will initially be approached at their pre-operative surgical visit by the surgical team about their potential interest in participating in the study. If they express interest, consent will be obtained by a surgeon involved in the study during the pre-operative clinic visit. If consent is unable to be obtained by the surgeon prior to surgery, it will be obtained on the day of surgery by a member of the Acute Pain Service to avoid the potential for perceived coercion – that somehow the performance of the operation will be dependent on their participation in the study.

Inclusion criteria shall be as follows:

- 1) Patient presenting for open or endoscopic septorhinoplasty
- 2) Age 18-80
- 3) Normal oral food and water intake before surgery
- 4) ASA physical classification 1-3

Exclusion criteria shall be as follows:

- 1) Refusal to consent
- 2) Patients without a cellular phone or who are unable to accept text messages
- 3) Allergy to opioid narcotics
- 4) ASA physical classification of 4 or higher
- 5) Patient requires other surgery in addition to septorhinoplasty
- 6) Age > 80 or <18
- 7) Any underlying chronic pain condition or ongoing opioid use over the preceding 3 months
- 8) Presence of any other factor which, at the discretion of any member of the study team, makes the patient a poor candidate for block placement.
- 9) Presence of any other factor which, at the discretion of any member of the study team, makes the patient a poor candidate for research participation.
- 10) Pregnant women

The ASA physical classification is a routine part of anesthesia pre-operative evaluation. This information will be extracted from the anesthesia pre-operative evaluation note.

Nerve block injections will be performed as described below under ‘study procedures’ by either faculty or fellows in the division of Acute and Perioperative Pain Medicine, who are part of the study team, under the direction of one of the faculty members.

STUDY PROCEDURES:

Those that consent to participate will be randomized to either

Group 1: a single injection into the pterygopalatine fossa bilaterally of 0.5% ropivacaine at a dose of 20 mg (each side) in 4-mL solution plus 1 mL of 4 mg dexamethasone. This will be done after the conclusion of the operation but prior to emergence from anesthesia

or

Group 2: a single injection into the pterygopalatine fossa bilaterally of a balanced crystalloid intravenous solution (4 ml of normal saline) plus 4 mg dexamethasone (each side). This will be done after the conclusion of the operation but prior to emergence from anesthesia.

During the block placement the surgical team will be asked to leave the operating room briefly so that they can remain blinded to the group assignment of all patients as the surgical team will manage the subjects post-operative care and determine discharge readiness.

The group 1 injection procedure will be performed as follows: after preparation of the skin using appropriate skin preparation solution and using aseptic technique, a small-gauge spinal needle will be advanced into the pterygopalatine fossa under ultrasound guidance. Once the needle is properly positioned, 0.5% ropivacaine will be administered at a dose of 20 mg plus 4 mg dexamethasone and the needle will be removed. This procedure will be performed bilaterally.

In group 2 the same procedure will be performed, but the injectate will consist of 5 mL of a balanced crystalloid intravenous solution (4 ml of normal saline) plus 1 mL of 4 mg dexamethasone (each side). This procedure will be performed bilaterally.

Four mL of balanced crystalloid solution plus 1 mL dexamethasone 4mg/mL was chosen as placebo therapy for the control group to aid in blinding since its appearance is identical to ropivacaine plus dexamethasone, to administer the dexamethasone to all patients in the same fashion, and to ensure that effects attributed to the block are a result of the administration of local anesthetic rather than compression neuropraxia from the injection of any material into the pterygopalatine fossa.

Additionally, after induction with general anesthesia, both group 1 and 2 will receive 8 mg of dexamethasone intravenously to reduce PONV and post-operative edema at the surgical site. Dexamethasone when added to nerve blocks has been demonstrated to be neuroprotective, and patients randomized to the placebo arm should also benefit from the neuroprotective effects of the perineural dexamethasone. This is being done in both groups to keep everything as controlled as possible and as mentioned above, to reduce post-operative nausea and vomiting and edema, which would be given regardless of study participation.

Both active treatment and placebo groups will receive bilateral injections of a total volume of 5 mL into the pterygopalatine fossa.

No other changes to the subject's clinical care will be made. All patients will receive the standard of care for pain management for septorhinoplasty, which is 3 days of opioid narcotics (typically oxycodone or hydrocodone) plus over the counter analgesics including acetaminophen and ibuprofen. All opioids will be prescribed as PRN. PACU nursing staff will be informed of patient's participation in the study but will not be informed as to group assignment so that they can remain blinded.

There will be no procedure note by the anesthesiologist describing the placement of the block. The anesthesiologist will write a note describing the subject's participation in the study with accompanying contact information in the event that the blind must be broken. A sign will also be placed at the head of bed indicating that the subject is a study participant and may have received the bilateral suprazygomatic maxillary nerve blockade with the PIs contact information. Data will be collected including, the time after leaving the operating room to first taking anything by mouth, at what time point did the patient first meet established readiness-for-discharge criteria (return to preoperative baseline oral food/liquid intake AND pain well-controlled with only oral medication) and at what time were they actually discharged. Additionally, information regarding pain scores and analgesic administration, both intraoperative and post-operative, will be gathered from the patient chart for the duration of their admission.

Patients will be sent a survey link via short message service (SMS) to their mobile device on POD 1, 3, and 5. Surveys will be created and distributed to participants using REDCap, a HIPAA compliant and secure platform, and distributed to participants through a third-party system Twilio. For security and privacy concerns, SMS transcriptions do not stay in Twilio's logs and are removed shortly after being completed. Surveys will be composed of 7 questions related to pain at its worst, pain at its least, average pain, current pain, as well as how many narcotic pain pills were consumed within the last 24 hours and what other pain medications were taken, ie acetaminophen, ibuprofen, etc. Relevant questions were adapted from the Brief Pain Inventory (short form) pain assessment. Data will be analyzed using the JMP statistical software package. Each survey will be the exact same set of questions. Patients will be advised to bring their opioid prescription bottle to their post-operative follow up visit and will be asked the same survey of questions during this visit. Additional data will be obtained through patient charting and may include any reported complications, PACU nurse notes, and phone calls to on call providers.

Outcome Measures:

The outcome measures for this study will be: decreased post-operative pain, reduced post anesthesia care unit recovery stays, and post-operative opioid use, as well as the morbidity that is associated with it, in patients undergoing septorhinoplasty surgery.

Table of Study Events

Table of Study Events

Activity	Screening	Pre-Op	Intra-Op	Post-Op
Consent	X			
Randomization		X		
Group 1: Suprazygomatic maxillary nerve block			X	
Group 2: Placebo injection with normal saline			X	
Data Collection				X
Data Analysis				X

STATISTICAL METHODS, DATA ANALYSIS, AND INTERPRETATION:

Data will be collected from the patient record regarding the primary and secondary study aims, as well as demographic information including age, sex, height, weight, and BMI on a daily basis for the duration of the hospital admission. Data will be analyzed using ANOVA, ANCOVA and mixed-models repeated-measures ANOVA techniques using the JMP statistical software package from SAS Labs.

Given that these outcomes, to the best of the study team's knowledge, have not been studied previously, no preliminary data exist on which to base power or sample size calculations, and this study is designed to collect such preliminary data on which future studies could be built. That being the case, there is no sample size calculation here. We request permission to enroll 50 patients per group into this study as previous studies involving similar blocks of the maxillary nerve have used group sizes of 20-30.

DATA STORAGE AND DE-IDENTIFICATION PLANS:

Protected health information will be accessed by study team members until data collection is complete, at which point all patients will be de-identified. All retained records will be stored on password-secured data storage devices in accordance with UF policies. Patient contact information stored within REDCap will include participants mobile phone number and medical record numbers. No other patient identifier will be inputted in the REDCap system such as name, date of birth.

7. Possible Discomforts and Risks:

As with any needle puncture of the skin, there is always a minute risk of infection or bleeding. In this case, there is a very limited number of structures within the pterygopalatine fossa. Those include the nerves being targeted by the block, the maxillary artery, and a small amount of fat. In this case, infection risk is minimized with chlorhexidine skin prep as would be used for surgery and the entire procedure is performed using aseptic technique. The risk of bleeding is extremely low. There is only one named vessel in the pterygopalatine fossa: the maxillary artery. This vessel is so small that it cannot routinely be identified on ultrasound, so contacting it with a needle is extremely rare. An inadvertent arterial puncture is one of minimal to no consequence given that both the pterygopalatine fossa is not a contained space and the needle being used is so small that any injury seals almost instantly. This approach makes inadvertent placement of the needle anywhere other than where it is intended extremely unlikely as there is a very limited number of structures within the pterygopalatine fossa. The only tissue along the needle path is the superficial tissue layers (skin, muscle), the tissues of interest, and bone. Needle contact with bone indicates that the needle should be withdrawn approximately 2mm and guiding the needle to be properly positioned. There is a risk of feeling pressure in the area of the block due to the injection of the nerve block as well as feelings of facial numbness due to the nerve block. All nerve blocks will be performed using real-time ultrasound guidance for visualization of the pterygopalatine fossa and the spread of the local anesthetic in the fossa.

Placement of saline:

As with any needle puncture of the skin, there is always a minute risk of infection or bleeding. In this case, infection risk is minimized with chlorhexidine skin prep as would be used for surgery and the entire procedure is performed using aseptic technique. The risk of bleeding is extremely low. There is a risk of feeling pressure in the area of the saline injection.

There is a risk of patient contact information being breeched, ie mobile phone number and medical record number, though risk is minimal. The REDCap platform is HIPAA compliant with a secure server. Database access requires user authentication and password login. REDCap and Twilio are both IRB and UF Privacy Office approved for collection and storage of PHI including surveys.

Data Safety Monitoring Board:

The PI and lead co-investigators (Drs. [name] and [name]) will meet at least once a month to review for any adverse events. A written report be generated.

8. Possible Benefits:

Participants randomized to the active nerve block arm can expect to experience less pain post-operatively. It is the hope of the investigators that this will also translate into decreased opioid consumption and a decrease in the number in opioid tablet prescriptions minimizing risk for potential abuse. If the findings are as expected, the investigators believe that this work may ultimately result in a change in the standard of care for patients undergoing septoplasty or septorhinoplasty, helping to improve patient comfort and safety.

9. Conflict of Interest:

No investigators have a conflict of interest.

References:

1. Sclafani, AP, et al. "Postoperative Pain and Analgesic Requirements after Septoplasty and Rhinoplasty." *The Laryngoscope*, U.S. National Library of Medicine, <https://pubmed.ncbi.nlm.nih.gov/30843623/>.
2. Wittekindt, D., et al. "Postoperative Pain Assessment after Septorhinoplasty - European Archives of Oto-Rhino-Laryngology." *SpringerLink*, Springer-Verlag, 1 Dec. 2011, <https://link.springer.com/article/10.1007/s00405-011-1854-x>.
3. Wang, Ping. "The Efficacy of Sphenopalatine Ganglion Block for Pain Management after Endoscopic Sinus Surgery: A Meta-Analysis of Randomized Controlled Studies - European Archives of Oto-Rhino-Laryngology." *SpringerLink*, Springer Berlin Heidelberg, 3 Jan. 2021, <https://link.springer.com/article/10.1007/s00405-020-06484-9>.
4. Kim, Do Hyun, et al. "The Effect of Sphenopalatine Block on the Postoperative Pain of Endoscopic Sinus Surgery: A Meta-Analysis." *Otolaryngology–Head and Neck Surgery*, vol. 160, no. 2, 2018, pp. 223–231., <https://doi.org/10.1177/0194599818805673>.
5. Watters, Carolina. "Septoplasty." *StatPearls [Internet]*., U.S. National Library of Medicine, 25 Oct. 2021, <https://www.ncbi.nlm.nih.gov/books/NBK567718/>.
6. Sclafani, Anthony P., et al. "Postoperative Pain and Analgesic Requirements after Septoplasty and Rhinoplasty." *The Laryngoscope*, vol. 129, no. 9, 2019, pp. 2020–2025., <https://doi.org/10.1002/lary.27913>.
7. Patel, Sagar, et al. "Opioid Use by Patients after Rhinoplasty." *JAMA Facial Plastic Surgery*, American Medical Association, 1 Jan. 2018, <https://www.ncbi.nlm.nih.gov/pmc/articles/PMC5833672/>.

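### Home opioid use is counted in pills of unfixed drug and strength, with no dose unit shared with the chart data, which costs precision and blurs the size of any effect

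*Combined protocol and SAP*

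**What the plan says.** Section 5 (Specific Aims) gives one primary aim, to "decrease the opioid requirement post-operatively". Outcome Measures in section 6 repeats post-operative opioid use as an outcome. Neither place gives a unit, a time window or a summary measure.

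Study Procedures in section 6 describes standard pain care as "which is 3 days of opioid narcotics (typically oxycodone or hydrocodone) plus over the counter analgesics including acetaminophen and ibuprofen", and adds "All opioids will be prescribed as PRN". No tablet strength appears.

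There are two sources of data on opioid use:

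- At home, patients get a "survey link via short message service (SMS) to their mobile device on POD 1, 3, and 5". The listed topics include "how many narcotic pain pills were consumed within the last 24 hours and what other pain medications were taken". None of them asks for the name or strength of the opioid. Patients are advised to bring the prescription bottle to follow-up, but the only stated activity there is to repeat the same questions.
- In hospital, "analgesic administration, both intraoperative and post-operative, will be gathered from the patient chart for the duration of their admission". No unit is named.

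Statistical Methods names ANOVA, ANCOVA and mixed-model repeated-measures ANOVA. It mentions no milligrams, morphine equivalents, conversion table, covariate for the drug prescribed, or rule for joining chart doses to pill counts.

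**The concern.** The aim concerns the amount of opioid needed, but the home instrument counts tablets. If tablets differ in drug or strength, two patients with the same opioid intake can report different counts, and two with the same count can have taken different amounts. Variation in what was prescribed then enters the outcome as noise unrelated to the block.

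Two things are at stake. The first is precision, in a trial of 50 per group with no sample size calculation behind it. The second is meaning. Statistical Methods says that the study is to supply preliminary data for later work, and a mean and SD in mixed pills cannot be carried to a site with another prescribing pattern. PACU opioid, given soon after the block, has no stated place on the same scale as home use.

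**Working it through.** The plan has no figure of its own to reproduce: it gives no alpha, power, effect size or SD. Everything below is for scale only.

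**Inputs.** From the documents: 50 per group; two typical home opioids; surveys on POD 1, 3 and 5 with 24-hour recall. Assumed: two-sided alpha 0.05; a 50:50 mix of two tablet types; one tablet worth r times the other (r from 1.25 to 3); coefficient of variation (CV) of the true dose, c, from 0.6 to 1.0; patients take as many tablets as reach the dose they need.

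**Precision.** Let pills = D/w, with D the true dose and w the worth of a tablet (1 or r), independent of D and of arm. The CV of 1/w is v = [(1 − 1/r)/2] / [(1 + 1/r)/2]. A given proportional reduction in dose gives the same proportional reduction in pills, so the required sample scales with the squared CV:

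variance ratio = [(1 + c²)(1 + v²) − 1] / c².

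For r = 1.5, v = 0.1667/0.8333 = 0.20 and v² = 0.04.

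- c = 1.0: 2 × 1.04 − 1 = 1.08.
- c = 0.6: (1.36 × 1.04 − 1)/0.36 = 0.4144/0.36 = 1.15.

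So 8–15% more patients are needed for the same power. As a reference, 50 per arm in a common dose unit gives 80% power for (1.960 + 0.842) × √(2/50) = 0.56 SD. For that same true effect measured in raw pills:

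| r | Variance ratio | Effective n per arm | Power |
|---|---|---|---|
| 1.25 | 1.02–1.05 | 48–49 | 0.78–0.79 |
| 1.5 | 1.08–1.15 | 43–46 | 0.74–0.77 |
| 2 | 1.22–1.42 | 35–41 | 0.65–0.72 |
| 3 | 1.50–1.94 | 26–33 | 0.52–0.63 |

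**Chance imbalance.** The SD of the between-arm difference in the share on one drug is √(2 × 0.25/50) = 0.10, or 10 points. Take a 1-SD imbalance (55:45 against 45:55), r = 1.5 and identical true need:

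- arm A: 0.55 × 1 + 0.45 × 0.6667 = 0.850 pills per unit of need;
- arm B: 0.45 × 1 + 0.55 × 0.6667 = 0.817;
- difference: 0.033/0.833 = 4%.

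A 2-SD imbalance gives 8%. At r = 3 the two figures are 10% and 20%. For comparison, the standard error of the arm difference in true dose is c × √(2/50), or 12–20% of the mean. The 4% equals v × √(2/50) = 0.20 × 0.20, so it is one draw from the noise already counted in the table, not a further error.

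**Can a total be formed?** If surveys arrive at about the same hour each day, the recalls cover the 24 hours ending on POD 1, 3 and 5. The periods from POD 1 to 2 and from POD 3 to 4 are not covered, so two of the five daily periods are missing. The POD 1 recall may also reach back into the hospital stay and count doses already in the chart. A common unit alone would therefore not give total use.

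**The case against.** A reader might infer that the pill count biases the trial or inflates type I error. The documents do not support that. Assignment is randomised, and the surgical team managing post-operative care is blinded, so drug and strength balance in expectation. Their variation sits in the between-patient error that the analysis already estimates.

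A reader might also infer that hospital and home use cannot be added. The text shows only that no rule for adding them is stated. The chart is already being extracted, the bottle comes to follow-up, and de-identification waits until data collection is complete.

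Nor can one say that a defined primary variable mixes units, because none is defined. Statistical Methods says that data on the aims come from the patient record, so the chart may be meant as the main source. That the chart holds doses is a reasonable inference, not stated text. Seven survey questions are announced and about six topics listed, so an unlisted item might ask for the drug, though nothing says so.

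Two further points stand. The 8–20% shifts need a 2-SD imbalance, and the 20% end needs every patient to be on either the weakest or the strongest assumed tablet. And if as-needed users take one tablet per pain episode whatever its strength, counts are not distorted in the way modelled, and conversion would bring prescriber choice into the outcome. Tablet numbers are also of interest in themselves: section 4 discusses how many are needed and prescribed, and section 8 hopes for fewer. These are reasons to keep the tablet count as a reported result. They do not remove the need for a dose unit when the aim is opioid requirement.

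The preliminary nature of the study lowers the stakes, but its declared use for later studies makes a portable unit more valuable.

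**Conclusion.** The concern holds as one of precision and interpretability. Followed as written, the home instrument counts unequal doses as equal, and the plan gives no unit shared by home and hospital use. At an assumed 1.5-fold difference between pills in a 50:50 mix, the cost is about 8–15% more patients for the same power, and a 1-SD imbalance in drug mix moves the pill comparison by about 4%. At a 2-fold difference the sample cost is 22–42%.

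These figures rest on assumed ratios, an assumed CV of 0.6–1.0, and patients adjusting tablet number to strength. The omission itself is certain from the text; its size is not. It should be corrected, but it is secondary to the lack of a defined primary endpoint.

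**What to change.** Before de-identification and unblinding:

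1. Record the drug, strength and number dispensed for each opioid prescription, from the chart or prescription record.
2. Convert PACU and home opioid to oral MME with one table named in the analysis plan, and run a sensitivity analysis with a second table.
3. Analyse MME for PACU and for each surveyed 24-hour period. Word the survey item, or define the derivation, so that PACU doses stay out of the POD 1 recall. Keep intraoperative opioid out of these outcomes, since the injection follows the operation.
4. Report a PACU-plus-home total only over a stated window, with home use taken as tablets dispensed minus tablets remaining in the bottle that patients already bring to follow-up.
5. Keep the raw tablet count as a reported secondary result.

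The cost is four fields per patient (drug, strength, number dispensed, number remaining), a conversion table, and a tablet count at an existing visit. Prescribing does not change. The drawback is that conversion factors are conventional, hence the second table, and the total is lost for patients who do not bring the bottle.

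### The POD 1 survey is sent by calendar day but its pill item looks back 24 hours from answering, so the post-operative hours it counts differ between patients

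*Combined protocol and SAP*

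**What the plan says.** Section 5 (Specific Aims) makes the primary aim to "decrease the opioid requirement post-operatively". For use at home, the defined measurement is the survey in Section 6 (Study Procedures): a "survey link via short message service (SMS) to their mobile device on POD 1, 3, and 5", which asks "how many narcotic pain pills were consumed within the last 24 hours". The wording does not change between days: "Each survey will be the exact same set of questions". The pain items are given no recall period.

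On time zero, the same section says of the injection: "This will be done after the conclusion of the operation but prior to emergence from anesthesia". The clock time of the block therefore depends on the operating list.

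On when an effect is expected, the Abstract cites maxillary blocks as reducing pain and "analgesic intake during the 24-hour period following endoscopic sinus surgery". The Background adds that pain after this surgery "is reported to be worse within the first 24-48 hours".

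No section states a send hour, a response window, a closing time or a rule for late answers. The Table of Study Events marks data collection only as post-operative.

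**The concern.** The survey is triggered by the calendar and its recall by the moment of answering, while the treatment effect runs from the block. None of these is tied to another. A patient operated on late who answers early next morning reports on well under 24 post-operative hours. A patient operated on early who answers late in the evening reports on a full 24 hours that leaves out the first part of recovery.

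This matters because the POD 1 count bears on the primary aim and is the only survey count that reaches the first 24 hours. The missed hours are not recovered later: the POD 3 recall starts well after the first day, and chart data stop at discharge. The trial is also meant to supply preliminary data for later studies, so a diluted POD 1 estimate would carry over into their planning.

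**Working it through.** The plan has no figure to reproduce. The 50 per group is set by precedent, with no stated effect size, SD or power. The check is one of timing.

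**Inputs from the protocol:** survey on POD 1, 3 and 5 (POD 1 read as the day after surgery); 24-hour recall for pills; block at the end of surgery; 24-hour period in the cited block evidence.

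**Assumed, not in the documents:** block between 09:00 and 17:00; POD 1 answer between 08:00 and 22:00.

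**Formulas**
- Hours from block to answer = 24 − block clock time + answer clock time.
- Start of recall relative to the block (offset) = hours from block to answer − 24.
- Overlap with the first 24 hours = max(0, 24 − |offset|).

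**Extremes**
- Block 17:00, answer 08:00: 24 − 17 + 8 = 15 h elapsed; offset −9 h; overlap 24 − 9 = 15 h.
- Block 09:00, answer 22:00: 24 − 9 + 22 = 37 h elapsed; offset +13 h; recall covers hours 13 to 37; overlap 24 − 13 = 11 h.
- Block and answer at the same clock hour: offset 0; overlap 24 h.

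**Overlap in hours on a grid of times**

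| Block | Answer 08:00 | 12:00 | 18:00 | 22:00 |
|---|---|---|---|---|
| 09:00 | 23 | 21 | 15 | 11 |
| 11:00 | 21 | 23 | 17 | 13 |
| 14:00 | 18 | 22 | 20 | 16 |
| 17:00 | 15 | 19 | 23 | 19 |

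The row sums are 70, 74, 76 and 76, so the mean is 296/16 = 18.5 h. Fourteen of the 16 cells are at 15 h or more. With both times uniform and independent over the assumed ranges, the mean is 19.8 h. About 36% of recalls then start before the block and about 36% start more than 4 h after it.

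**Late answers to the POD 1 link**
- At 12:00 on POD 2, a block at 17:00 gives 43 h elapsed, offset 19 h and overlap 5 h. A block at 09:00 gives 51 h elapsed and overlap 0.
- At 22:00 on POD 2, even a 17:00 block gives 53 h elapsed and overlap 0.

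**Can POD 3 fill the gap?** Elapsed time runs from 72 − 17 + 8 = 63 h to 72 − 9 + 22 = 85 h, so recall starts at hour 39 to 61. It does not reach the first day.

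**With the message anchored** and answers within an assumed ±2 h of 24 h, the same 24-hour item would cover 22 to 24 of the first 24 hours, mean 23.0 (96%).

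**Illustration only.** Take 50 per group, two-sided alpha 0.05, an assumed standardised difference of 0.5 and an effect confined to the first 24 hours. Scaling the difference by the mean share captured (19.8/24 = 0.83, or 0.96 if anchored) gives power of about 54% with open timing and 67% with anchoring, against 70.5% with full capture. The scaling holds the SD fixed. A shorter count would also have a smaller SD, so the loss may be overstated.

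**The case against.** The strongest reply is that most plausible answers still cover most of the first day, that the study is preliminary, and that no POD 1 endpoint is named as primary. The coverage point is right and limits the size of the problem. It does not remove it, because coverage still varies by up to 13 of 24 hours among answers given on the correct day.

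Early use is also partly recorded elsewhere. The chart holds analgesics and pain scores through the admission, and patients are asked to bring the opioid bottle to follow-up. This offsets the problem only in part: the chart stops at discharge, no bottle count is defined, and no rule joins these sources to the survey.

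Several stronger readings are tempting, but the documents do not support them:
- **Bias by arm.** A reader might infer that pain or sedation shifts response time differently in the two arms. Nothing in the plan links response time to arm. Surgeons and PACU staff are blinded and both arms get the same survey schedule.
- **Pre-operative pills in the count.** Ongoing opioid users are excluded, so hours before surgery should add about no pills. They only shorten the post-operative time counted.
- **PACU doses counted twice.** This could happen, but no section says that chart and survey doses are to be added.
- **POD 1 as the only survey that could show any effect.** The protocol defines no effect window, and the Background mentions "effects on pain for up to 10 days after injection". That statement is cited to a study listed as tonsil infiltration, so it is weak support for this block, but it rules out an absolute claim.

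**Conclusion.** The point holds as a matter of measurement precision. The calendar-day trigger and the 24-hour look-back together make the POD 1 opioid count refer to different post-operative periods in different patients. Under the assumed clock times it covers 11 to 24 of the first 24 hours, on average 18.5 h on the grid or 19.8 h with uniform times, and less when the answer slips to POD 2. The consequence is noise and some dilution of the POD 1 arm difference. Directional bias is not shown.

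The hours depend on assumed list and answering times, which the sponsor can replace with its own. The missing anchor does not depend on those assumptions. The power figures are illustrative. This should be changed, since a better schedule costs almost nothing, but it does not invalidate the trial.

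**What to change.** 1. Schedule the REDCap/Twilio messages by time since the injection: about 24, 72 and 120 hours. For daytime surgery each falls at the same clock hour as the block.
2. Record the block time, or operating-room exit as a proxy, and the completion time of every survey. Block time is not among the listed data, and there is to be no block procedure note. Completion times would also serve the secondary objective on the SMS survey.
3. Keep all answers. Analyse them by actual hours since the block, for example as a covariate, with a sensitivity analysis restricted to answers near the target time. Report response times by arm. Closing the link and setting late answers to missing would discard usable data, and a closing window of several hours would still admit shifted recall.
4. On POD 1, ask for tablets taken since leaving the hospital and add charted opioid doses from block to discharge, in a common unit. The total then runs from block to answer with no gap or double count, and a difference in discharge time between arms moves doses between sources without changing the total.
5. State a recall period for the pain items.

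**Cost:** each patient needs a start time entered to trigger the messages. The POD 1 pill item would differ from the later surveys, so the statement that all surveys are identical must be amended and the repeated-measures analysis must allow for it. No extra patients or visits are needed.
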